2. STUDY SCHEDULE AND TIMELINE

IBSOS is a prospective, randomized, multi-site clinical trial comparing three types of psychotherapy delivered in an individual format for severely affected adults with IBS. After a four-week baseline data collection period, participants will be randomly assigned to receive either four-session self-administered CBT, 10-session therapist-administered CBT or a control condition emphasizing support and education (allocation 1:1:1). The acute treatment phase will last 10 weeks. Participants will undergo follow-up examinations two weeks after treatment ends (week 12) and three, six, nine, and 12 months after the end of treatment.

IBSOS requires the expeditious enrollment of a sufficient number of participants to ensure the statistical power and generalization of study results. This trial plans to recruit 480 participants over an approximately four-year treatment delivery period. Assuming a relatively conservative pre randomization dropout rate of 25%, each site will need to phone telephone screen approximately 150 participants per year and enroll (consent) 75 in order to meet yearly recruitment quotas of 60 randomized participants at each site.

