2.1 Duration of Study and Visit Schedule

After a one-year clinical trial planning phase, the study will begin recruitment of 480 Rome diagnosed adults. Recruitment is scheduled to occur over 48 months. The acute treatment phase will be administered over 10 weeks. Participants assigned to standard CBT will attend 10 weekly sessions. Participants assigned to either the limited contact or attention control treatments will attend four clinic visits scheduled over 10 weeks. Participants will undergo post-treatment evaluation two weeks after their assigned treatment ends (week 12) and at quarterly intervals (three, six, nine, 12 months) out to 12 months. Follow-up of all participants will continue until the last participant randomized has completed 12 months of follow-up.

See Appendix 1: IBSOS Protocol Overview

See Appendix 2: IBSOS Detailed Work Flow

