3.2 Secondary Objectives

Aim 2. To identify clinically useful participant characteristics associated with outcome as a way of gaining an understanding of subgroups of participants for whom CBT is most beneficial.

Hypothesis 1: Variables such as treatment motivation at baseline and rapid treatment response will be positively associated with treatment outcome after the acute treatment phase of CBT and through follow-up periods.

Hypothesis 2: Interpersonal distress and extra-intestinal medical problems at baseline will be negatively associated with treatment outcome after the acute treatment phase of CBT and through follow up.

Aim 3. To identify theory-based change mechanisms (active ingredients) that explain how and why CBT achieves therapeutic objectives.

Hypothesis 1: Changes in the severity of IBS symptoms are partly mediated by changes in participants' beliefs regarding the causality (locus of control) and controllability (self efficacy) of IBS symptoms.

Hypothesis 2: Changes in the severity of IBS symptoms are partly mediated by nonspecific factors such as a strong therapeutic alliance and positive expectancy of improvement.

Aim 4. To describe the cost and cost effectiveness of MC-CBT, S-CBT and attention placebo for IBS.

Hypothesis 1: MC-CBT is associated with decreased direct and indirect cost compared to SCBT and associated with increased direct and indirect cost compared to attention control.

Hypothesis 2: MC-CBT will prove cost effective relative to either S-CBT or attention control.

Aim 5. To assess long-term durability of acute treatment effects of CBT at 3-, 6-, 9-, and 12 month follow-ups.

Hypothesis: Participants assigned to both CBT conditions will maintain treatment gains with respect to attention placebo through quarterly follow-up periods extending to 12 months after treatment completion.

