1.0 and the growth parameter variance at 1 (all creating a rough approximation to standardized effects). For a linear growth curve, statistical power of 0.80 is achieved with a sample size of approximately 75 per group in a two-group contrast of growth curves, and power of 0.90 is achieved for a sample size of approximately 95 per group. For a quadratic growth curve, the sample size required under the same conditions for power of 0.80 is approximately 90 per group and for power of 0.90 it is approximately 110 per group. These estimates map favorably onto the sample sizes for the proposed research.

In sum, we will use traditional analysis of covariance to compare the treatment groups at a given point in time and growth curve modeling to compare the decay functions in groups after treatment.

Figure 1. Basic Growth Curve Model

Equivalence Testing

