- Interim assessment Participants will describe their daily bowel habits using the Bristol Stool form and rate the intensity of pain, bloating, and urgency (11-point VAS) at the end of each day through the 10-week acute treatment phase. At the end of each week of the acute treatment phase, they will rate global symptom severity, satisfaction with IBS symptoms, life interference, and mood using the abbreviated POMS, and time spent completing homework assignments. In addition, participants will complete process measures (IBS SE, WAI, IBS LOC, etc) at regularly scheduled times during active treatment phases. Participants should complete process measures within seven days of their being assigned.

- Two-week follow-up assessment The two-week assessment should occur two weeks from the date of the last active treatment session, plus or minus (+) two weeks.
- Three-month assessment The three-month assessment should occur three months ± two weeks from the date of the last active treatment session.
- Six-month assessment The six-month assessment should occur six months \pm two weeks from the date of the last active treatment session.
- Nine-month assessment The nine-month assessment should occur nine months ± two weeks from the date of the last active treatment session.
- 12-month assessment The 12-month assessment should occur 12 months \pm two weeks from the date of the last active treatment session.

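### The Appendix 7 follow-up schedule puts the 12-month visit at week 52, about 9.7 months after treatment ends, while Section 2 and Appendix 8 require 12 months after treatment, about week 62

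*Protocol*

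**What the plan says.** Section 2 fixes the length of treatment: "The acute treatment phase will last 10 weeks". It then lists follow-up two weeks after treatment (week 12) and "three, six, nine, and 12 months after the end of treatment". Section 2.1 confirms the origin of the week count by equating week 12 with the visit two weeks after treatment ends, so week 10 is the end of treatment.

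Aim 5 in Section 3.2 sets the durability horizon as "quarterly follow-up periods extending to 12 months after treatment completion". The safety introduction in Appendix 9 likewise has quarterly follow-up running for one year from the end of treatment.

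Appendix 8, under Study Visit Windows, gives the operational rule: "The 12-month assessment should occur 12 months", with a tolerance of "two weeks from the date of the last active treatment session".

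The Book 3 forms schedule in Appendix 7 has a Months row (1, 3, 6, 9, 12) above a Weeks row. On both of its pages the Weeks row reads 12, 22, 34, 46, 52.

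**The concern.** A site cannot satisfy both the forms schedule and the visit window for the final visit. A visit booked from the Weeks row would fall well outside the window the protocol sets for it.

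This visit is the last point of the Aim 5 analysis of how treatment effects decay after treatment. It is also the last time point for the secondary endpoints in Section 3.4 that run through 12 months or at quarterly follow-ups. If the visit takes place at week 52, results reported as 12 months after treatment would describe about 9.7 months. The outcome at the intended time could not be recovered afterwards.

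**Working it through.** **Inputs.** Treatment ends at week 10 (Section 2; consistent with week 12 being two weeks later in Section 2.1). The target is 12 months ± 2 weeks after the last session (Appendix 8). Book 3 weeks are 22, 34, 46 and 52 for months 3, 6, 9 and 12. One calendar month = 365.25 / 12 / 7 = 4.348 weeks.

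**Step 1: where the text puts each visit.** Target week = 10 + months × 4.348; window = target ± 2.

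| Month | Book 3 week | Target week | Window | Book 3 week against window |
|---|---|---|---|---|
| 3 | 22 | 23.0 | 21.0–25.0 | inside |
| 6 | 34 | 36.1 | 34.1–38.1 | 0.1 week early |
| 9 | 46 | 49.1 | 47.1–51.1 | 1.1 weeks early |
| 12 | 52 | 62.2 | 60.2–64.2 | 8.2 weeks early |

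**Step 2: what week 52 means.** 52 − 10 = 42 weeks, and 42 / 4.348 = 9.66 months after treatment. It is 62.2 − 52 = 10.2 weeks before the 12-month target but only 52 − 49.1 = 2.9 weeks after the nine-month target. It lies in neither window.

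**Step 3: can one counting rule produce the row?**

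- Four-week months from week 10: 10 + 4 × months = 22, 34, 46, 58. The first three match exactly and the last does not. Even on this rule the 12-month window would be weeks 56–60, which excludes 52.
- Calendar months from the start of treatment: 52 / 4.348 = 11.96 months, so week 52 fits. But weeks 22, 34 and 46 would then be 5.06, 7.82 and 10.58 months, which do not fit 3, 6 and 9.
- The gaps between successive visits are 10, 12, 12 and 6 weeks. The last is 6 / 4.348 = 1.4 months where a quarter is intended.

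No single rule gives the row. The likeliest explanation is that week 52 was taken as one year from the start of treatment, but the protocol does not say so.

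**Step 4: does the exact end of treatment matter?** With the last session at week 9, 10, 11 or 12, week 52 is 9.89, 9.66, 9.43 or 9.20 months later. The 12-month window opens at week 59.2, 60.2, 61.2 or 62.2. Week 52 is outside it every time.

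**The case against.** The strongest reply is that this is one slipped column header. Appendix 7 is a checklist of forms, the same column is also labelled month 12, and Appendix 8 states the visit rule clearly. The trial has two sites with shared training, bi-weekly calls and central consistency checks, so staff may well follow the windows. That is fair as to likelihood: nothing in the protocol shows that visits would be held at week 52 or that the sites would differ. It does not remove the contradiction, which concerns the scheduled date of a main assessment. Appendix 8 allows windows to be extended only as an exception, which cannot cover a planned date 8 weeks early.

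The Appendix 7 tables were also read poorly from the PDF, and the month labels on one page are scrambled. A misread digit cannot be excluded, but 52 appears on both pages, so it is unlikely.

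A reader might infer more than the protocol supports:

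- **That the growth model assumes equally spaced visits.** The duration of 4 and frequency of 1 in Section 7.4 are inputs to the power calculation. The protocol fixes no time scores for the analysis and allows nonlinear and spline trajectories.
- **That decay slopes would be biased by 18%.** If a straight decline were observed at weeks 12, 22, 34, 46, 52 but coded as 12, 23, 36, 49, 62, the fitted slope would be 1309.6 / 1589.2 = 0.824 of the true one. That requires every visit to follow the table and every analysis to use the text's nominal times. The same rescaling would then apply to all arms. The two sets of times correlate at 1309.6 / √(1092.8 × 1589.2) = 0.994, so under a simple linear model with independent errors comparisons between arms would lose little precision. It is not an expected effect.
- **That counting from the last session makes timing differ between arms.** All three treatments are planned over 10 weeks, and the protocol gives no figure showing differential timing. Counting from the end of treatment suits a question about durability after treatment, so another anchor would be a design preference.

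**Conclusion.** The inconsistency is real and specific. Book 3 dates the final follow-up at 42 weeks (9.7 months) after treatment; Sections 2 and 3.2 and Appendices 8 and 9 require 12 months. The gap is about 10 weeks against the target and about 8 weeks against the opening of the window. The conclusion rests on treatment ending at week 10, on calendar months, and on 52 being read correctly. It survives last sessions at weeks 9 to 12 and four-week months.

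One sentence under Follow-Up in Appendix 9, which speaks of up to five follow-ups in the 12 months after sign-on, leans towards an earlier end date. It conflicts with the other statements and does not settle the matter.

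The damage, if visits followed the table, would be a mislabelled horizon for Aim 5 and the 12-month secondary endpoints. A biased comparison between arms is not shown. The primary endpoint in Section 3.3 carries no assessment time, so the finding does not bear on its definition. The small shortfalls at weeks 34 and 46 come from four-week months and are minor.

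**What to change.** Give the final visit one date. Either change the Book 3 Weeks row, on both pages, to agree with the definition in Section 2 and Appendix 8 (about week 62), or keep week 52 and change every statement and window that places the visit 12 months after treatment. In the same edit, check weeks 34 and 46 against their windows and align the follow-up sentence in Appendix 9.

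The first route costs one table row on two pages and one sentence. The second touches Sections 2, 2.1 and 3.2, the Appendix 4 inclusion criterion on follow-up contact, and Appendices 8 and 9, and it shortens the durability claim.

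As an optional safeguard, the growth curves could be fitted to time computed from recorded visit dates, so that any visits held off schedule are analysed at their true times.

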APPENDIX 9: Human Subjects Protection

Informed Consent

Because the study will rely on intent to treat (ITT) (vs. completer) approach for data interpretation, all randomized participants will be included in study analyses. Therefore, it is important to have information on as many participants as possible. If a participant is unwilling to continue full engagement in the study, every effort should be made to strongly encourage the participant to undergo regularly scheduled follow-up clinic evaluations, and, if this is impossible, a minimum-level contact (telephone interview).

Documenting Withdrawal of Consent

If a participant indicates that s/he wishes to withdraw consent, his/her wish must be honored. Just as it is a severe ethical breach to enroll a participant without her consent, so it is a severe ethical breach not to honor her withdrawal of consent. At all times during this process, the participant should be treated with the utmost respect and courtesy. This is his/her due, of course, but also, participants sometimes change their minds and may return to the study if they are shown respect and courtesy.

Procedures for Discontinuation

A participant's decision to withdraw from a clinical trial should be documented in the study records using the Off Study (i.e. drop out) Form. At a minimum, such documentation should include:

- Whether the discontinuation of the participant's participation resulted from a decision by the participant or by the investigator;
- Whether the discontinuation involves some (e.g. treatment but not follow up assessments) or all types of participation;
- The reason for the discontinuation.

An individual report should be promptly submitted to the site IRB if the discontinuation was related to an unanticipated problem involving serious risks to the participant. Otherwise, premature discontinuations can be summarized in regularly scheduled reports for DSMB.

Follow-Up

Once participants have signed on to the study, we become responsible for following them up to five times over the following 12 months — regardless of whether they enter or complete treatment. The first challenge is simply maintaining contact; the second is getting them to come in and complete the assessments.

All potential candidates for the study will be given a current copy of the IRB-approved Informed Consent Form to read. The PI investigator, sub-investigators or their designees (e.g. supervised graduate students, research coordinator, project coordinator) will explain all aspects of the study in lay language and answer all of the candidate's questions regarding the study. If the candidate desires to participate in the study, s/he will be asked to sign the Informed Consent. Informed consent is obtained from each participant before they are enrolled in the study. The consent form describes the potential risk and benefits of study participation as well as the responsibilities of the participants and the investigators. Participants who refuse to participate or who withdraw from the study will be treated without prejudice. In the event a significant protocol change occurs, the informed consent should be modified appropriately and sites will need to submit the revised documents to their IRB for approval. It should be noted that the overall content of initial consent form submitted for IRB approval at each site will be standard across clinical sites. It may be necessary to address unique questions/issues raised by the local IRB boards in the consent forms. Nevertheless, we will endeavor to maximize consistency in content across all consent forms.

Participant Safety and Confidentiality

Introduction

The psychosocial interventions consist of individual cognitive behavioral therapy or supportive counseling. The acute treatment phase will last 10 weeks with follow-up periods occurring every three months for one year following the end of treatment. Neither psychosocial treatment is expected to pose any particular risk. Each Site Investigator has primary responsibility for the individual participants under his or her care.

Protocol review and study monitoring

An independent Data and Safety Monitoring Board (DSMB) is appointed by NIDDK and is charged with monitoring the progress of the study. The DSMB reviews and approves the protocol prior to study initiation. During the study, the DSMB meets biannually (one face-to-face, one telephone conference) to review study progress and trouble shoot around any problems that threaten study aims. These reviews include evaluation of interim data as well as the monitoring of participant safety and the quality of all aspects of study operations.

The PI and Site Investigators continually monitor safety issues at his/her site and report any problem to the Administrative Core at the University at Buffalo. As noted in the Chapter on Trial Governance, the IBSOS will identify a safety officer who functions as an independent evaluator (external to the study) of all adverse events (AEs), both serious and non-serious. In the case of this unmasked trial, the safety officer will work with the investigators to assure that the event is fully documented. Safety officers also review adverse event data to assess if the frequency of the AEs changes dramatically from baseline during treatment delivery phase of the trial. This change could be across the study or a change in the AE profile at a specific site.

Exclusions

Persons with medical or psychological contraindications will be deemed ineligible to be enrolled.

Institutional Review

Prior to study implementation, the protocol, informed consent forms, and all advertising materials must be approved by the IRB of each participating study site. All protocol amendments effecting the safety and welfare of study participants must be approved by the IRB prior to implementation. The study site PI is responsible for all submission documents and for periodic review reports required by the IRB.

Data Security and Confidentiality

All participant information, and even the fact that an individual is participating in the study, is considered confidential. This confidentiality is assured in IBSOS through several mechanisms. First, each participant is assigned an anonymous study ID, which is then used on all study forms. Second, all study forms, and paper records that contain participant information (e.g. consent forms, address lists, phone lists) are kept in secured, locked areas when not in use. In addition, such materials, when in use, are kept away from public scrutiny. Materials and specimens that can be discarded are destroyed. Third, access to all participant data and information, including laboratory specimens, is restricted to authorized personnel. In the case of computerized data, this restricted access is assured in several ways. At the clinical centers, the data are maintained on personal computers (PCs) that are password-protected. Staff members receive individualized account numbers and passwords that allow them access only to those elements of the data management system to which they are authorized. At the Administrative Core, access to computerized data is restricted in two ways. First, only authorized personnel are granted access to the data, and, second, this access is further restricted by password protection.

When the study database is made available to clinical centers and to the Project Office, it does not include actual identities and contact information of participants. Such information is retained at the individual clinical centers for use in the event that future follow-up of the study participants is necessary. Finally, participants are not identified by name in any reports or publications, nor are data presented in such a way that the identity of individual participants can be inferred.

All members of the research team are required to complete a confidentiality certification procedure upon employment. Policies regarding the confidential nature of the data collected, processed and stored are explained to all personnel who must then sign a "confidentiality certification" before being allowed access to confidential information.

The CC and each SI will continually reinforce the need for careful and confidential handling of data at staff meetings and trainings. In addition, key personnel are required annually to sign a confidentiality statement affirming that they agree to abide by the Center for Health Research's policies on research confidentiality and ethics.

Protection of Participant Privacy

Privacy in the context of this study includes confidentially of data and personal information at the participating sites and in the handling and reporting of data obtained by sites. It also includes discretion of the part of the clinical center staff and

arrangements or physical privacy during interviews and examinations. Each site is responsible for ensuring physical privacy of participants and ensuring that data are stored in a secured area accessible only to IBSOS staff. These provisions and arrangements will be monitored during periodic visits from the CC.

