3.1 Primary Objective

Aim 1. To evaluate the efficacy of MC-CBT compared to S-CBT and attention control for IBS.

Hypothesis 1: Both MC-CBT and S-CBT are superior to attention-control on the primary endpoint of global improvement of IBS symptoms and secondary endpoints of satisfactory relief of IBS symptoms, quality of life, change in stool consistency, psychological distress, IBS symptom severity, participant satisfaction, and health care use.

Hypothesis 2: Equivalence testing will show that MC-CBT does not differ from S-CBT on primary (global IBS symptom improvement) or secondary endpoints.

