A premise of the proposed research is that the brief version of CBT (MC-CBT) for IBS will be about as effective as the extended version (S-CBT). A problem with traditional null hypothesis testing is that one can never accept the null hypothesis; i.e., one can never declare that two means or two average growth curves are exactly equal. All one can do is fail to reject the null hypothesis. The problem of declaring equivalence between treatments has been addressed in the statistical literature on bio-equivalence testing and we will adapt this perspective in the current research. The spirit of the approach is to specify an *a priori* population threshold value (TV) where meaningful differences between groups can be said to emerge. To take a commonplace example, if we compare the annual incomes of males and females and the mean difference in salary is \$3, this is a trivial difference that for all practical purposes does not matter. The mean annual salaries are "functionally equivalent." However, a mean difference in annual income of \$3,000 is meaningful and has important implications for the lifestyles of the two groups. The key to equivalence testing is specifying a TV such that if a population difference is between -TV and +TV, then one concludes that the group difference is trivial and that the two groups are "functionally equivalent." If the population difference exceeds +TV or is lower than -TV, then the groups are declared nonequivalent. Equivalence testing is implemented by testing two directional hypotheses with respect to a predefined value of TV using standard tests of significance; one hypothesis that the population mean difference is greater than -TV and the other that

the population mean difference is less than +TV. If both null hypotheses are rejected relative to the alternative hypotheses, then one is confident that the true population difference is somewhere between -TV and +TV. This leads to a formal assertion of functional equivalence in the groups. A statistically equivalent form of this test is to compute confidence intervals about the mean difference in the sample data. If the upper limit of the interval is less than +TV and the lower limit of the interval is greater than -TV, then functional equivalence is declared.

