The issues involved in applying equivalence testing are well known and discussed in Wellek ¹⁵. The confidence interval approach can be easily adapted to comparing adjusted mean differences in the analysis of covariance framework described earlier, as well as comparing decay functions in the growth curve analyses. A key issue in this portion of the research is the development and specification of conceptually and empirically justifiable threshold values. For example, for the IBS-SS scale, it is commonly argued that a 50-point reduction represents the cutoff for meaningful change¹⁹. This suggests that a TV of 50, such that if the population mean difference between the treatments is between -50 and +50, then the interventions are deemed functionally equivalent. Stated more formally, if the lower limit of the relevant confidence interval for the mean difference in the sample data is greater than -50 and if the upper limit is less than +50, then the interventions are declared functionally equivalent. Our previous research with the IBS-SS yielded scores that ranged from 82 to 422 with a standard deviation of approximately 78. The estimated half-width of a 95% confidence interval for a two group mean difference with a sample size of 160 per group (using a tolerance value of 90%) is approximately 18, indicating our sample size will yield interval widths that are viable for making statements of functional equivalence for this measure. As another example, the accepted standard in the field for a clinically meaningful change on the IBS Quality of Life measure (which ranged from 15 to 92 in our previous work, with a standard deviation of 19.5) is 14 units ²⁰. If two treatments yield a population difference between -14 and 14, then they can be declared functionally equivalent. The estimated half-width of a 95% confidence interval for this measure given our sample size is approximately 4, again indicating our sample sizes can sustain this type of analysis. The statistical and methodological issues for building empirical support for threshold values can be complex and are discussed elsewhere ^{21, 22}.

Aims 2 and 3

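### The protocol chooses ITT over a completer approach for all interpretation, but ITT need not be conservative for the MC-CBT versus S-CBT equivalence test, so a supportive adherent-set analysis should stand beside it

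*Protocol*

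**What the plan says.** Protocol Appendix 9 (Human Subjects Protection, under Informed Consent) states that "the study will rely on intent to treat (ITT) (vs. completer) approach for data interpretation" and that "all randomized participants will be included in study analyses". It names the completer alternative, sets it aside, and makes no exception for any hypothesis.

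Section 3.1, Hypothesis 2, plans an equivalence claim: "Equivalence testing will show that MC-CBT does not differ from S-CBT on primary (global IBS symptom improvement) or secondary endpoints". Section 7.4 makes comparability of the two CBT formats the main focus of Aim 1 and pursues it by conventional testing and by equivalence testing. The equivalence rule is a confidence interval lying inside a threshold value (TV): "If the upper limit of the interval is less than +TV and the lower limit of the interval is greater than -TV, then functional equivalence" may be claimed. For the IBS-SS the threshold is applied as "if the population mean difference between the treatments is between -50 and +50, then the interventions are deemed functionally equivalent".

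The equivalence text names no analysis set, and no per-protocol or adherent-set analysis appears anywhere in the protocol. Section 7.3 mentions ITT, missing data and attrition only as preliminary topics. Appendix 8 (Study Visit Windows) has everyone followed for outcome whether or not therapy was completed. No post-randomization non-completion rate is stated; the 25% in Sections 2 and 4.3 is dropout before randomization.

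**The concern.** For the two superiority contrasts against attention control, keeping non-completers in their assigned arms normally works against the claim. For equivalence it can work in favour of the claim, because anything that shrinks the contrast moves the estimate away from the margin.

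Several features of this trial make that plausible. Section 6 describes the CBT arms as two doses of one therapy, 10 sessions against four. Someone who leaves S-CBT early has had a contact level closer to that of MC-CBT. Section 8.2 puts the number of sessions that most psychotherapy patients attend at six, below the 10 planned for S-CBT. Because non-completers remain in follow-up, their outcomes enter the contrast.

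At stake is what a positive equivalence result would mean. It could show that assigning patients to either format gives similar results. It could also be read as showing that the two treatments work equally well when received, which ITT alone does not establish.

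**Working it through.** **Inputs from Section 7.4.** The IBS-SS "yielded scores that ranged from 82 to 422 with a standard deviation of approximately 78", with margin ±50. The IBS-QOL has SD 19.5 and margin ±14. There are 160 participants per group, with a 95% interval.

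**The plan's own figure.** Section 7.4 puts the IBS-SS half-width at about 18; up to that number, its wording is "95% confidence interval for a two group mean difference with a sample size of 160 per group (using a tolerance value of 90%) is approximately".
- SE = 78 × √(2/160) = 8.72.
- Half-width = 1.96 × 8.72 = 17.1, or 17.2 with the t quantile.
- With the 90% tolerance factor √(χ²(0.90; 318)/318), the half-width is 18.02. The stated figure reproduces.
- IBS-QOL: SE = 19.5 × √(2/160) = 2.18, half-width 4.27 (4.50 with tolerance), consistent with the stated value of about 4.

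No figure in the plan is wrong. The point concerns the analysis set.

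**Illustration of dilution.** Let f be the share of participants with no between-arm difference (assumed, 0 to 30%), and let Δ be the true difference among the rest. Then
- ITT difference d = Δ × (1 − f);
- P(equivalence declared) = Φ((TV − d)/SE − 1.96) − Φ((−TV − d)/SE + 1.96). The second term is negligible here.

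With Δ exactly at the margin, for the IBS-SS:

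| f | d | (50 − d)/8.72 − 1.96 | P |
|---|---|---|---|
| 0 | 50 | −1.96 | 2.5% |
| 10% | 45 | −1.39 | 8.3% |
| 20% | 40 | −0.81 | 20.8% |
| 30% | 35 | −0.24 | 40.5% |

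The same calculation for the IBS-QOL (Δ = 14) gives 2.5%, 9.4%, 25.0% and 48.7%.

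**How quickly it fades (IBS-SS).**

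| True difference | f = 10% | f = 20% | f = 30% |
|---|---|---|---|
| 55 | 2.9% | 10.2% | 26.1% |
| 62.5 | 0.4% | 2.5% | 10.7% |
| 75 | <0.1% | 0.1% | 1.2% |

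**Primary endpoint.** Section 7.4 works through margins only for the two scales above, so the responder endpoint needs an assumed margin. Assume 60% response in S-CBT and a true difference at the margin. At f = 10%, 20% and 30%, a 15-point margin gives 4.6%, 7.8% and 12.6%; a 20-point margin gives 5.5%, 10.9% and 19.1%. The pattern is the same but weaker.

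**The direction can reverse.** Assume gains of 100 points in S-CBT and 50 in MC-CBT, no gain in non-completers, and non-completion of 10% in S-CBT and 30% in MC-CBT. The ITT difference is 100 × 0.9 − 50 × 0.7 = 90 − 35 = 55, larger than the 50 among completers.

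**Precision of an adherent-set analysis.** If 30% are excluded, 160 × 0.7 = 112 remain per arm. SE = 78 × √(2/112) = 10.4 and the half-width is 20.4 against a margin of 50. Power at zero difference is 99.5%.

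**The case against.** **The SAP may cover it.** Supportive analysis sets are often left to the SAP, which is not shown. The ITT sentence sits in a passage whose purpose is retention. A reader might infer that the protocol forbids any analysis but ITT for equivalence. The documents do not support that: the equivalence text names no set, and nothing excludes a supportive one. What remains is that the protocol makes a positive choice of ITT over completers for all interpretation, without a carve-out. An SAP that added such a set would have to be squared with that wording.

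**The direction is not established.** A reader might infer that ITT will dilute a real difference in this trial. The documents do not show this either. Section 8.2 concedes that MC-CBT asks more effort of participants at home. Under Appendix 6, two consecutive missed sessions count as non-compliance in either CBT arm, which is half of MC-CBT but a fifth of S-CBT. If MC-CBT non-adherence is the greater, ITT can widen the contrast, as the 55-point example shows. Nor is an early S-CBT leaver the same as an MC-CBT recipient, whose four visits cover the full range of techniques with self-study materials. This objection stands and limits the point to a possibility.

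**ITT answers the trial's question.** The trial compares delivery systems, and failure to finish 10 weekly visits is part of S-CBT as delivered. That also stands, and it is why ITT should remain primary.

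**An attendance-defined set is imperfect.** It loses the protection of randomization, the thresholds for four and 10 sessions are not directly comparable, and attendance misses home study. This is a good reason not to let it overrule ITT. It does not argue against reporting it as support.

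**Conclusion.** The point holds as a modest, inexpensive improvement. The protocol's stated reliance on ITT is valid for the effect of assignment but not necessarily conservative for the equivalence of MC-CBT and S-CBT, and no analysis is named that would show whether the conclusion depends on non-completion.

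The size is conditional. The rise from 2.5% to about 8%, 21% and 41% on the IBS-SS assumes that 10%, 20% or 30% of participants have no between-arm difference. It also assumes a true difference among the rest exactly at 50 points (50/78 = 0.64 SD, above the d = 0.50 used for power in Section 7.4). The IBS-SS is a secondary measure. Well beyond the margin the risk is small: about 1% at a difference of 75 with 30% affected. It would be wrong to conclude that ITT is the wrong primary analysis, that a false equivalence claim is likely, or that an adherent-set result should veto an ITT result.

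**What to change.** Keep ITT as the primary analysis for every contrast, and leave the superiority comparisons with attention control unchanged. For MC-CBT versus S-CBT only:

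1. Pre-specify a supportive adherent-set analysis, with minimum attendance defined separately for each arm before outcome data are seen.
2. Report it beside the ITT result, with the same interval and threshold values.
3. If the two disagree, limit the conclusion to equivalence of assignment to the two delivery formats, and do not claim equal efficacy when the treatment is received.
4. Amend the Appendix 9 sentence so that it allows for this supportive analysis.

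The cost is one additional analysis and a definition. Therapists already record attendance and homework adherence (Appendix 8, Homework Compliance), so no new data collection is needed. The downside is that the adherent set is smaller and not fully protected by randomization, which is why it should be supportive only.
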